2.0 LIST OF ABBREVIATIONS

APS	American Physiological Society
CD	Cluster of differentiation
GERD	Gastroesophageal reflux disease
GCP	Good clinical practice
GLP	Good laboratory practice
H2RA	H2 receptor antagonists
IBD	Inflammatory bowel disease
IL	Interleukin
LEC	Local Ethics Committee
M1	Macrophage type 1
M2	Macrophage type 2
NERD	Non-erosive reflux disease
pCRF	Paper Case Report Form
PPIs	Proton-pump inhibitors
Th1	Type 1 T-helper
Th2	Type 2 T-helper
TNF α	Tumor necrosis factor alpha
TNF β	Tumor necrosis factor beta

3.0 INTRODUCTION

Gastroesophageal reflux disease (GERD) is one of the most common diseases and, according to recent epidemiological studies, clinical and endoscopic GERD symptoms can be detected in 8-25% of the population depending on country, race and gender [1]. Although GERD rarely is a cause of death, it is associated with prominent morbidity and complications, such as esophageal ulceration, peptic stricture, Barrett's esophagus and therefore leading cause of esophageal adenocarcinoma [2].

In the Russian Federation, the prevalence of GERD reaches 11-15% [2]. The incidence of GERD in the past 15 years has increased significantly and is currently 5 per 1000 population per year [1].

Despite improvements in diagnostics and treatment of GERD, there are still many unresolved issues. An example of a diagnostic challenge is identifying patients with non-erosive reflux disease (NERD), which has been documented to occur in 50-60 % of GERD patients. These patients periodically or continuously complain on heartburn, while they do not have endoscopic evidence of esophagitis.

Another challenge concerns patients suffering from refractory GERD, who despite treatment do not improve clinically and/or endoscopically, but on the contrary, progress to more extensive erosion, ulceration and esophageal complications such as peptic esophageal stricture, bleeding, and Barrett's esophagus which constitutes a precancerous disease [4].

In GERD, damage of the esophageal mucosa may occur as a result of activity of different types of refluxate, i.e. gastric, biliary or duodenogastric/mixed. Along with acid and pepsin, duodenal contents with duodenogastric reflux may be harmful to the esophageal mucosa. Previous studies demonstrate that conjugated bile acids produce fewer harmful effects than deconjugated bile acids in a more neutral pH environment [24]. Although proton pump inhibitors may weaken both acid and duodenogastric reflux by decreasing its volume, their prescription not always adequately addresses or eliminates the cause of the disease.

In recent years, the study of refractory GERD at the tissue and cellular level, which is based on the study of esophageal mucosal injury depending on the nature of the refluxate (gastric, biliary or duodenogastric/mixed) has increasingly become an area of interest particularly also in the light of investigating the immune response in patients with GERD. For instance, it appears that patients with high levels of interleukin-8 (IL-8) have a higher risk of recurrent GERD [5], and patients with high levels of IL-1b have a higher risk of torpid course of GERD [6].

Cytokines, important for cell signaling, are mainly produced by macrophages. Macrophages may change their phenotype under influence of different factors (known as macrophage plasticity). Macrophages produce not only inflammatory and anti-inflammatory cytokines, but also growth factors and reactive oxygen species (superoxide radical anions, singlet oxygen, hydrogen peroxide), which define immune response of the whole body [7].

GERD is characterized by disorders in the immune response as presented by misbalanced cellular (Th1) and humoral (Th2) parts of immune response, which might be determined by different phenotypes of macrophages – M1 (pro-inflammatory) or M2 (anti-inflammatory). Previous studies have shown that the activation of Th1-immune response leads to the erosive form of GERD, whereas activation of Th2- immune response may lead to the development of Barrett's esophagus [8, 9].

4.0 RATIONALE

According to the published data, type of esophageal injury and its mucosal response greatly depends on the nature/type of refluxate (gastric, biliary or duodenogastric/mixed) and patient immune profiles [6]. It has been shown that Th-2-predominant cytokine response leads to Barrett's esophagus. Also it was shown that acid suppression and alkaline duodenal reflux may increase the risk of Barrett's esophagus [23].

We hypothesize that the different types of refluxate may somehow differentiate macrophage phenotype and thereby the immune profile, determining the type of GERD disease and its progression.

This study is proposed to evaluate the role of motoric dysfunctions and burden of different kinds of refluxate on immune cells and the subsequent course of the disease. This study also aims to establish a bridge between instrumental findings (pH-impedance test) and clinical assessments (FSSG questionnaire), aiming to facilitate the use of simple questionnaire techniques in the clinical setting in the future.

This study will potentially also provide further insight and input into future uses and indications for prokinetics in GERD and may aid in improving the treatment concepts of GERD and complications thereof (Barrett's oesophagus).

5.0 PROGRAM OBJECTIVE(S)

5. 1. Study Objectives:

Animal (*in vitro*)-part of the study:

1. To determine changes of macrophage phenotype and macrophage plasticity in mice, particularly C57/BL6 genetic strain after exposure to gastric refluxate (human origin)
2. To determine changes of macrophage phenotype and macrophage plasticity in mice, particularly C57/BL6 genetic strain after exposure to biliary refluxate (human origin)

3. To determine changes of macrophage phenotype and macrophage plasticity in mice, particularly C57/BL6 genetic strain after exposure to duodenogastric/mixed refluxate (human origin).

Clinical (patients) part of the study

1. To investigate blood and biopsy-origin monocyte/macrophage phenotype in patients with different forms of acid reflux disease (non-erosive GERD (NERD), erosive GERD and complications thereof: Barrett's esophagus)
2. To investigate types of refluxate (gastric, biliary, duodenogastric/mixed) in patients with different forms of acid reflux disease (non-erosive GERD (NERD), erosive GERD and complications thereof: Barrett's esophagus)
3. To investigate the relationship between clinical assessments (FSSG questionnaire) and measurements obtained from esophageal pH-impedance monitoring and esophageal high-resolution manometry.

5.2. Primary Endpoint

Animal (*in vitro*) part of the study:

To determine changes in macrophagal phenotype from baseline after exposure to three different forms of refluxate (gastric, biliary duodenogastric/mixed) by means of assessing:

- a) Morphological characteristics (quantity of M1 (round forms) and M2 (fibroblasts-like) macrophages on 100 analyzing cells in 5 non-interfering sights).
- b) Macrophagal phagocytosis activity (mean percentage of phagocytizing cells in all peritoneal macrophagal cells and mean number of bacteria ingested by macrophages)
- c) Secretory activity (ratio of proinflammatory M1 cytokines IL-1 β , IL-8, IL-12p70, IFN γ , TNF α and TNF β to anti-inflammatory M2 cytokines IL-4, IL-5 и IL-10, as well as M1/M2 cytokines IL-2 и IL-6).

- d) Receptor characteristics (ratio of superficial markers CD80 and CD 25 (M1-markers) and CD206 and CD163 (M2-markers). Changes in M1 and M2 ratios determined on the base of receptors will also be analyzed.

Clinical (patients) part of the study:

- 1. Characteristics of blood and biopsy-origin monocyte/macrophage phenotype (morphology, receptor characteristics) in patients with different types of acid reflux disease (NERD, erosive GERD) and complications thereof: Barrett's esophagus).
- 2. Number of patients with gastric, biliary, duodenogastric/mixed refluxate within each of the different patient groups (NERD, erosive GERD and complications thereof: Barrett's esophagus).
- 3. Mean FSSG scores (acid reflux related symptoms, dysmotility symptoms) in patients with gastric, duodenogastric/mixed reflux related to the three different patient subgroups (NERD, erosive GERD and complications thereof: Barrett's esophagus).

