6.5. Program Conduct

[figure not shown]
This is a prospective, experimental study consisting of the two parts: a clinical (patients) part and an animal (in vitro) part.

The clinical (patients) part of the study will be conducted at the Propaedeutic Clinic of Internal medicine, Gastroenterology, Hepatology of First MGMU n.a. IM Sechenov.

The animal part of the study (in vitro) will be conducted at the Moscow State University of Medicine and Dentistry.

The in vitro part of the study will be conducted in M1 macrophages from mice of genetic line C57/BL6 (90 ± 15 mice). To mirror the design of clinical part of the study and to ensure compliance with the enrolled patients' number macrophages from 30 ± 5 mice will be exposed to acid refluxate, macrophages from another 30 ± 5 mice – to biliary refluxate and from the other 30 ± 5 mice – to mixed refluxate.

Figure 1. Study design

	Visit 1	Visit 2	Visit 3	Visit 4	Visit 5
Timelines and Allowance Window	Day 1 Baseline	Day 2 (±1Day)	Day 3 (±2 Days)	Day 4 (±2 Days)	Day 5
Signed informed consent	X				
Assignment of patient identification number	X				
Inclusion and exclusion criteria assessment	X				
Allocation to the subgroups of GERD			X		
Demographics (date of birth, gender, race)	X				
Medical history	X				
Physical examination	X	X	X	X	X
FSSG assessment	X				
Blood sampling (macrophages)		X			
Hematology (RW, HIV, HbsAg, HCV)		X			
Upper gastrointestinal endoscopy with biopsy and collection of refluxate			X		
24-h esophageal pH-impedance test with esophageal high-resolution manometry				X	
Safety assessments*	X	X	X	X	X

* Any safety issues related to the invasive study procedures

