The functional macrophage phenotype was estimated by cytokine (pro-inflammatory, such as IL-12 (M1 markers) and anti-inflammatory, such as IL-10 (M2 markers)) production [22]. Cytokine concentrations will be defined by flow cytometry [Beckman Coulter FC500, USA] with multiplex definition kits. The functional phenotype of macrophage population will be estimated as a ratio of functional markers of M1 and M2 phenotypes.

Determination of macrophage phenotype after exposure to human acid refluclate, human biliary refluclate and mixed human refluclate will be performed by the above mentioned methods (the part of "Determination of macrophage phenotype") and the changes vs initial results will be registered.

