9.0 STATISTICAL METHODS

This is an experimental, interventional, non-randomized study. The primary purpose of the this study is exploratory in its general sense and no hypothesis is being tested, therefore no sample size calculation was performed.

Planned enrollment in this study constitutes 90 patients in clinical part and 90 subjects (mice) in animal (in vitro) part.

Statistical analysis will be performed using the STATISTICA 8.0 software for Windows (StatSoft Inc, the USA).

Normality of data distribution will be tested by using either the Shapiro-Wilk or Kolmogorov-Smirnov test.

In case of normal (Gaussian) distribution of data significance of differences will be determined by Student's t-test. In cases with non-normal distribution we will use non-parametrical U-test according to the method of Mann-Whitney for independent samples.

Tests resulting in p-values less than or equal to 0.05 will be reported as "statistically significant».

Continuous data will be summarized using descriptive statistics, and the following parameters will be reported: number of observations (n), mean and standard deviation (SD); minimum (Min), and maximum (Max); median. 95 % CI will be calculated.

Categorical data will be presented using frequency (n) and percentage (%).

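### The animal part asks whether refluxate types differ but specifies only a change within each type, and Section 9.0 does not say which groups its two-sample tests compare

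*Combined protocol and SAP*

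**What the plan says.** The question is comparative. Section 4.0 (Rationale) states: "We hypothesize that the different types of refluxate may somehow differentiate macrophage phenotype and thereby the immune profile".

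The animal part does not carry that comparison through:

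- Section 5.1 gives three animal objectives, one per refluxate. The first concerns macrophage change "after exposure to gastric refluxate (human origin"; the other two repeat the wording for biliary and for mixed refluxate. None mentions another type.
- Section 5.2 defines the animal primary endpoint as "To determine changes in macrophagal phenotype from baseline after exposure to three different forms of refluxate", assessed through four families of readouts (morphology, phagocytosis, secretion, receptors).
- Section 6.6, on phenotype after exposure, says that "the changes vs initial results will be registered".
- Section 6.5 uses separate animals for each type: "macrophages from 30 ± 5 mice will be exposed to acid refluxate, macrophages from another 30 ± 5 mice – to biliary refluxate", with a third set for mixed refluxate.

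Section 9.0 describes the study as exploratory with no hypothesis tested. It names Student's t-test (paired or unpaired not stated) or, for non-normal data, the Mann-Whitney test for independent samples. It does not tie either test to an endpoint or a pair of groups, and it names no test for three groups. It adds: "Tests resulting in p-values less than or equal to 0.05 will be reported as" statistically significant.

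**The concern.** A change from the initial value within one refluxate type answers whether that refluxate does anything. It does not answer whether gastric, biliary and mixed refluxate do different things, which is what the Rationale asks. The plan leaves two ways to reach an answer, and neither is sound as it stands.

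Under the first, each type gets its own verdict at 0.05. A significant change for one type beside a non-significant change for another is not evidence that the two differ.

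Under the second, the tests are applied between types, two at a time. With three types and no adjustment, the chance of finding some difference by accident exceeds 5%.

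The animal part is where refluxate type is assigned rather than observed, so it is the most direct evidence the study will have on its own hypothesis.

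**Working it through.** **Inputs.** From the documents: 30 ± 5 mice per type in separate sets (Section 6.5), and a 0.05 threshold per test (Section 9.0). Assumed: two-sided tests, normal data with equal SD, independent mice, one readout. Effect sizes are in SDs of the change and are assumptions, because the documents give none.

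**The plan's own figure.** There is no power or sample-size calculation to reproduce. 3 × 30 = 90 (75 to 105 with ± 5) agrees with the planned 90 ± 15 mice.

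**Reading 1: three within-type verdicts.** Let p be the power of one within-type test (one-sample t-test on the change, noncentral t). If all three types have the same true change, the chance that at least one verdict is significant and at least one is not is

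1 − p³ − (1 − p)³.

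With n = 30 (last column from unrounded p):

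| Common true change (SD) | p | Verdicts disagree |
|---|---|---|
| 0 | 0.050 | 14% |
| 0.2 | 0.185 | 45% |
| 0.36 | 0.479 | 75% |
| 0.5 | 0.754 | 56% |
| 0.53 | 0.801 | 48% |
| 0.8 | 0.988 | 3% |

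At p = 0.5 the formula gives 1 − 0.125 − 0.125 = 0.75, its maximum. At 0.5 SD the figure is 66% with 25 mice per type and 44% with 35. Simulation (40,000 studies per setting) agreed: 45%, 75%, 56% and 3% at 0.2, 0.36, 0.5 and 0.8 SD.

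**Reading 2: three unadjusted pairwise t-tests between types.** In the same simulations, with identical true changes, at least one pair reached p ≤ 0.05 in 12.1% to 12.3% of studies. This is below the 1 − 0.95³ = 14.3% for three independent tests because the pairs share groups.

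**Direct three-group comparison.** A one-way analysis of the same simulated changes rejected in 4.8% to 5.1% of studies.

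**What a direct comparison can detect.** For one pair of types at 80% power, the difference is (1.960 + 0.842) × √(2/n):

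- n = 30: 2.802 × 0.258 = 0.72 SD
- n = 25: 0.79 SD
- n = 35: 0.67 SD

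A within-type change needs only 2.802/√30 = 0.51 SD by the same approximation.

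**The case against.** The strongest reply is that the plan never commits the faulty inference. A reader might infer that the sponsor will call types different because one p-value falls below 0.05 and another does not, and that the conclusion will therefore often be wrong. The documents do not support that. No section states such a rule, and the Mann-Whitney test for independent samples fits type against type better than change from baseline. A direct comparison is thus open under the plan. This stands, and the disagreement rates describe only what would follow if separate verdicts were compared.

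Three further replies have weight:

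- **Exploratory status.** Section 9.0 says no hypothesis is tested, and describing each change is a legitimate exploratory aim. This lowers the stakes. It does not make separate verdicts an answer to a comparative question, and results will still carry a significance label.
- **The 75% is a ceiling.** It occurs only at 50% power. At 0.8 SD the figure is about 3%.
- **Planned intervals help.** With true changes of 0.8, 0.8 and 1.6 SD, all three verdicts are significant in 98% of simulated studies, while the three-group test finds the difference in 89%. Section 9.0 also plans 95% CIs. At n = 30 these are about ± 0.37 SD, giving on average 0.43 to 1.17 and 1.23 to 1.97, which do not overlap. An attentive reader would see that difference.

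What remains after these replies is that the favourable reading leads to unadjusted pairwise tests among three groups, and no section names the contrast that addresses the hypothesis.

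**Conclusion.** The point holds in a limited form. The hypothesis is about a difference between refluxate types; the animal objectives and primary endpoint specify only within-type changes; and Section 9.0 supplies two-sample tests without saying which groups they compare. The result is either three verdicts that cannot answer the question or three unadjusted pairwise tests with about a 12% false-difference rate per readout, where a single three-group test would hold about 5%.

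The rates rest on normal data, equal SDs, 30 mice per type and one readout. They also assume independent mice. The refluxate is of human origin, and the documents do not say how many donors supply each type or whether one donor's sample is used for several mice. If donors are shared, neither the 5% nor the 12% can be relied on.

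**What to change.** In Section 5.2 (animal part) and Section 9.0:

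1. Add the between-type difference in change, for each readout, as the comparison that addresses the hypothesis.
2. Test it with a one-way analysis of the changes across the three types, or Kruskal-Wallis if the data are not normal. Make pairwise comparisons only if that test is significant, and report differences with 95% CIs.
3. Keep the three within-type changes as estimates with 95% CIs, and state that a type difference will not be inferred from separate p-values.
4. Record which donor's refluxate each mouse's cells receive. If donors are shared across mice, account for this in the analysis.

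The cost is wording plus one analysis per readout on the same mice and data. There are two limits to state openly. A between-type difference is harder to show than a within-type change (about 0.72 SD against 0.51 SD at 80% power, n = 30). Error control also applies per readout only; across the readouts in the four families the animal part remains exploratory.

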FSSG (Frequency Scale for the Symptoms of GERD) – questionnaire with 12 questions related to acid reflux and dysmotility symptoms (See Appendix A). Questions 2,3,5, 8 and 11 are related to 'dysmotility', while other questions consider acid reflux symptoms. FSSG allows investigators to analyze different symptoms experienced by GERD patients [10]. Sum of both parts of the questionnaire will be analyzed for each patient. Permission to use the questionnaire for this study was obtained from its author/developer, professor [name].

- **Safety Assessments**

Any AEs related to the invasive study procedures, will be collected. Only undesirable effects that are deemed at least possibly related to an Abbott medication by the investigator will be forwarded to Abbott affiliate PV.

Visit 2

- **Physical examination**

Includes the measurement of blood pressure, pulse

- **Hematology (RW, HIV, Hbs-Ag, HCV)**

Blood tests for RW, HIV, Hbs-Ag, HCV are mandatory and considered standard of medical care before any interventional procedures are performed (such as endoscopy and pH-impedancemetry).

- **Blood sampling (monocytes/macrophages)**

The protocol of monocytes/macrophages isolation from venous blood

1. Blood will be collected in previously marked Vacuette system test tube (10-12 ml)
2. Blood in the test tube will be mixed with heparin (1 ml heparin – 10 ml blood)
3. Transportation of the marked test tubes in the laboratory of Cellular Biotechnology of Moscow State University of Medicine and Dentistry. The samples will be stored at temperature $+4\pm2^{\circ}\text{C}$ until transportation and will be transported in a mobile refrigerator ($+4\pm2^{\circ}\text{C}$) to the laboratory of Cellular Biotechnology of Moscow State University of Medicine and Dentistry. Laboratory address: [name]
4. Blood sample is stirred and placed into centrifuge.

5. Blood sample is centrifuged for 15 minutes at 3000 rpm.
6. After centrifugation the supernatant is separated from blood clot, in blood clot leukocytes are separated from erythrocytes, and leukocytes are placed in a pure plastic test tube.
7. Lysis buffer is prepared: 100 ml of distilled water per 0.825 g NH4Cl, 0.0037 g EDTA.
8. The leukocyte mass is mixed with 10 ml of lysis-buffer and mixed in vortex for 5 minutes (40 rpm).
9. The test tube is centrifuged for 4 min – 1000 rpm.
10. The supernatant is separated and drawn away.

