The refluxate samples required for the animal (in vitro) part of the study, will be placed into pure plastic test tubes and be stored at temperature +2-4 C until transportation to the Cellular Biotechnology of Moscow State University of Medicine and Dentistry. Transportation should be done at the temperature +2-4 C and be done within two hours after obtaining the refluxate.

- **Allocation to the subgroups of GERD**

Diagnosis of GERD (non-erosive and erosive) is made based on clinical symptoms (complaints of heartburn, regurgitation, belching, (non-cardiac) chest pain) and/or the results of an upper gastrointestinal endoscopy. Endoscopy should not have been done more than a month before inclusion. Diagnosis of Barrett's esophagus has to be endoscopically confirmed (incl. biopsy) and should not be older than 6 months prior to study enrolment.

Patients included into the study with a GERD diagnosis based on symptoms only and/or with an endoscopy performed more than one month ago prior to inclusion will be allocated to the subgroups on the result of endoscopy conducted at Visit 3.

- **Safety Assessments**

Information regarding complications of the procedure and patient complaints are to be collected and registered. After the procedure each patient will be placed under medical observation for at least for two hours. Any AEs related to the invasive study procedures, will be collected.

Only undesirable effects that are deemed at least possibly related to an Abbott medication by the investigator will be forwarded to Abbott affiliate PV

Visit 4

- **Physical examination**

Includes the measurement of blood pressure, pulse.

- **24-h esophageal pH-impedance test with esophageal high-resolution manometry**

To investigate number of reflux episodes and determine the type of refluxate (gastric, biliary, duodenogastric/mixed) in patients with different forms of acid reflux disease and complications thereof (Barrett's esophagus) pH-impedance test with esophageal high-resolution manometry (HRM) will be done.

Calibration of device by means of two standard buffer solutions at temperature 37 C is necessary before the 24-hr esophageal pH-impedance test is performed.

Procedure of pH impedance includes intranasal introduction of a probe into oesophagus and connection of the probe with the recording device and 24-hour wearing of the probe. Installation of the probe is carried out on an empty stomach.

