High-resolution manometry (HRM) will be done with a 22-channel water-perfused catheter and Solar GI system (Medical Measurements Systems, Enschede, the Netherlands).

In GERD patients will be analyzed following HRM parameters: the distal contractile integral (DCI) and the lower esophageal sphincter resting pressure (LES RP).

24-h pH-impedance monitoring will be done in both distal oesophagus and in the stomach according to standard of practice. Esophageal pH sensor will be positioned 5 cm above the manometrically located border of the LES. Measurement with a second pH sensor in the stomach, 10cm below the LES in order to monitor intragastric acidity will be done as a standard routine procedure.

The probe is removed after 24 hours and the results from the recording unit are transferred to the computer database for further analysis.

Standard measuring parameters will be collected: percent of time when pH is less than 4, total number of reflux episodes, number of acid and alkaline reflux episodes, duration of longest reflux episode.

• Safety Assessments

Information regarding complications of the procedure and patient complaints are collected and registered. After the procedure each patient is placed under medical observation for at least two hours. Any AEs related to the invasive study procedures, will be collected. Only undesirable effects that are deemed at least possibly related to an Abbott medication by the investigator will be forwarded to Abbott affiliate PV

Visit 5

- Removing of the device for 24-h esophageal pH-impedance test.

The results from the recording unit are transferred to the computer database for further analysis.

- Physical examination

Includes the measurement of blood pressure, pulse.

- Safety Assessments

Information regarding complications of the procedure and patient complaints are collected and registered. Any AEs related to the invasive study procedures, will be collected. Only undesirable effects that are deemed at least possibly related to an Abbott medication by the investigator will be forwarded to Abbott affiliate PV.

Conduct of the Animal (in-vitro) part of the study.

The animal part of the study will be conducted in accordance with all applicable regulatory requirements: International Guiding Principles for Biomedical Research Involving Animal, APS's Guiding Principles in the Care and Use of Vertebrate Animals in Research and Training, Good Laboratory Practice.

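### Endpoint 3 relates FSSG to a refluxate category that omits biliary, and no planned analysis relates FSSG to the manometry readings that objective 3 names

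*Combined protocol and SAP*

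**What the plan says.** Clinical objective 3 in Section 5.1 reads "To investigate the relationship between clinical assessments (FSSG questionnaire) and measurements obtained from esophageal pH-impedance monitoring and esophageal high-resolution manometry". It names both instruments.

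In Section 5.2 the only clinical endpoint that uses FSSG is item 3: "Mean FSSG scores (acid reflux related symptoms, dysmotility symptoms) in patients with gastric, duodenogastric/mixed reflux related to the three different patient subgroups". Item 2 just above it uses a longer refluxate list: "Number of patients with gastric, biliary, duodenogastric/mixed refluxate within each of the different patient groups". Clinical objective 2 uses the same three types, and so does the Visit 4 text in Section 6.6, where the purpose of the test is to "determine the type of refluxate (gastric, biliary, duodenogastric/mixed) in patients with different forms of acid reflux disease".

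Section 6.6 (Visit 4) names the readings. For manometry it says that two parameters will be analysed: "the distal contractile integral (DCI) and the lower esophageal sphincter resting pressure (LES RP"). For pH-impedance it lists "percent of time when pH is less than 4, total number of reflux episodes, number of acid and alkaline reflux episodes", and then the duration of the longest episode. On FSSG, the Visit 1 text says "Sum of both parts of the questionnaire will be analyzed for each patient".

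Section 9.0 provides descriptive summaries with 95% confidence intervals, Student's t-test for normally distributed data, and otherwise the "non-parametrical U-test according to the method of Mann-Whitney for independent samples". It also declares the study exploratory, with no hypothesis tested.

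**The concern.** A stated objective should lead to an endpoint and then to an analysis. For objective 3 that chain is complete only for refluxate type. Nothing says how FSSG will be set against the manometry parameters, so that half of the objective will either go unanswered or be answered by a method chosen after the data are seen.

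The refluxate lists raise a second problem. A patient typed as biliary is counted in endpoint 2 but belongs to no cell of endpoint 3, and no text explains the exclusion or pools that patient with the mixed type. Both items stand under the heading of primary endpoints, so the denominators of two primary endpoints would differ without a stated reason.

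**Working it through.** The plan gives no figure to reproduce here. The check is a comparison of texts, followed by a short calculation of what the proposed analysis would cost and deliver.

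**Objective against endpoint and analysis**

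| What objective 3 asks FSSG to be related to | Readings named in Section 6.6, Visit 4 | Linked to FSSG in an endpoint or analysis? |
|---|---|---|
| pH-impedance, as a category | Refluxate type | Yes, endpoint 3, but for 2 of 3 types |
| pH-impedance, as quantities | % time pH<4; total, acid and alkaline episodes; longest episode (5) | No (0 of 5) |
| Manometry | DCI, LES resting pressure (2) | No (0 of 2) |

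**Could Section 9.0 fill the manometry row?** Both named tests compare two groups. To apply them, either FSSG or a manometry parameter would have to be split in two. The documents define no FSSG cut-off and no grouping of DCI or LES resting pressure. No correlation, regression or other method of association is named.

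**Refluxate lists.** Clinical objective 2, clinical endpoint 2 and the Visit 4 purpose statement name gastric, biliary and duodenogastric/mixed. Endpoint 3 names gastric and duodenogastric/mixed. One of three types is missing. How many patients this affects cannot be stated from the documents. Restoring biliary takes the table from 3 × 2 = 6 cells to 3 × 3 = 9. With 90 patients the average per cell falls from 90/6 = 15 (if all patients were of the two listed types) to 90/9 = 10.

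**Number of estimates needed**
- FSSG scores: 7 acid-reflux items scored 0–4 (range 0–28), 5 dysmotility items (0–20), total 0–48 (Section 6.6, Visit 1, and Appendix A).
- Core set: 2 subscores × 2 manometry parameters = 4 pairs, or 3 × 2 = 6 with the total.
- Optional set: 2 × 5 = 10 further pairs for the quantitative pH-impedance readings, or 3 × 5 = 15 with the total, making 14 or 21 pairs in all.

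**If each pair were labelled at 0.05.** With all pairs null and independent, the chance of at least one flag is 1 − 0.95^k. This gives 1 − 0.95^4 = 0.185, 1 − 0.95^6 = 0.265 and 1 − 0.95^21 = 0.659. These are upper illustrations: the scores and readings are correlated, and the total is the exact sum of the two subscores.

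**Precision of one correlation.** The interval is tanh[atanh(r) ± 1.96 × √((1 + r²/2)/(n − 3))], Fisher z with the Bonett-Wright variance. The value r = 0.3 is an assumption. The sizes follow from 30 ± 5 per group.
- n = 75: 0.07 to 0.50.
- n = 90: √(1.045/87) = 0.1096, and 0.3095 ± 0.2148 gives 0.09 to 0.48.
- n = 105: 0.11 to 0.47.

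Adjusting for three disease groups replaces n − 3 with n − 5. At n = 90 the interval is still 0.09 to 0.48.

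**The case against.** The study is declared exploratory, and no test decision, error rate or safety question depends on this. Comparing mean FSSG between refluxate types is a legitimate way to investigate a relationship with pH-impedance, and the descriptive statistics and two-group tests in Section 9.0 support it. The Rationale (Section 4.0) describes the bridge to FSSG for the pH-impedance test only. The missing biliary type may be a drafting slip, and a long list of extra correlations would be heavier than the gap.

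Much of this stands, and it sets the limits of the point. A reader might infer that endpoint 3 does not address objective 3 at all. That goes too far, because refluxate type is itself determined at the Visit 4 test. A reader might also infer that the manometry data will go unanalysed. Section 6.6 says that both parameters will be analysed; it does not say against what. Nor are the FSSG scores of biliary patients left wholly unused, since the Visit 1 text says the sum of both parts is analysed for each patient. Correlating the five quantitative pH-impedance readings as well would be a preference rather than a correction.

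What does not stand is exploratory status as a full answer. Section 9.0 uses it to explain the absence of a sample size calculation. It does not explain why a stated objective lacks an analysis. Section 5.1 names manometry explicitly, whatever the Rationale leaves out.

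**Conclusion.** The point holds in two limited parts. First, neither manometry parameter is related to FSSG in any endpoint or analysis, and Section 9.0 has no method that could do so without a grouping that the plan does not define. Second, endpoint 3 omits one of the three refluxate types used elsewhere, and the passages must be reconciled. Restoring the word alone would not make the table workable, because no text gives the rule that turns the Visit 4 readings into one refluxate type per patient.

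The change is worth making, but the severity is modest. The conclusion rests on the wording of Sections 5.1, 5.2, 6.6 and 9.0 and on no numerical assumption. The intervals above depend on an assumed correlation of 0.3 and describe the proposed analysis, not the size of the defect.

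**What to change.** 1. In Section 5.2, add biliary to clinical endpoint 3, or state how those patients are handled in it. State the rule that assigns each patient one refluxate type from the Visit 4 test. Keep the table of means as descriptive.
2. Add to endpoint 3 and Section 9.0: Spearman correlations with 95% confidence intervals of the FSSG acid-reflux and dysmotility subscores with DCI and LES resting pressure, on all patients with data. Include the total score if that is what the Visit 1 sentence on the sum of both parts means, and say so. Give each correlation unadjusted and adjusted for disease group (partial rank correlation), since patients are recruited in three groups of fixed size and a pooled correlation could reflect differences between groups.
3. If wanted, list the quantitative pH-impedance readings as a secondary set.
4. Report all of these as exploratory estimates, without the statistical significance label that Section 9.0 attaches to p-values of 0.05 or less.

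The cost is wording and a small amount of analysis. All the readings are already planned to be collected, so no new procedure or visit is needed. The downside is more to interpret: 4 to 6 core pairs, or 8 to 12 estimates with the adjusted versions, and thinner cells in the endpoint 3 table if biliary becomes a third type.
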